7.5.2.1 Liver function tests

Descriptive summary of PCS values in Liver Enzymes and Total Bilirubin will be provided as per Astellas standard TLB_005.

In addition, a matrix scatter plot of Liver Enzymes and Bilirubin will be plotted showing the maximum ALT, AST, ALP and total bilirubin during the Safety Emergent Period crossed against each other. Different dots will be used for roxadustat and ESA.

Individual displays of Liver Enzymes and Bilirubin parameters, listed in Section [6.2.3.1](#) will be reported for all subjects with either ALT or AST > 3 x ULN or total bilirubin > 2 x ULN during the Safety Emergent Period.

For subjects who require further liver function investigations, additional information will be collected and listed.

7.5.3 Vital Signs

Descriptive and changes from baseline for vital signs (systolic blood pressure, diastolic blood pressure, respiratory rate, weight and pulse) at each assessment time point and for the maximum and minimum on-treatment (i.e during Safety Emergent Period) value will be presented by treatment arm and type of ESA treatment.

Maximum on-treatment value will be determined using all the original values and not the derived windows.

A plot for each parameter of mean (+/- 95% CI) versus visit will be produced by treatment arm (two arms in one page) and type of ESA treatment (darbepoetin alfa and epoetin alfa in another page) for pre-dialysis and post-dialysis values.

PCS Vital signs criteria (10 Combined) will be analyzed in the same way as explained in Section [7.5.2](#) for PCS laboratory abnormalities.

All vital signs data will also be listed.

7.5.4 Electrocardiograms (ECGs)

Descriptive and changes from baseline for ECG parameters (Pulse, PR Interval, RR Interval, QRS interval, QT interval, and QTc interval) at each assessment time point and for the maximum - on-treatment (i.e during Safety Emergent Period) value will be presented by treatment arm and type of ESA treatment.

Maximum on-treatment value will be determined using all the original values and not the derived windows.

The number and percentage of subjects with post-baseline PCS values (see [Table 9](#) and [Table 10](#)) will be tabulated by treatment group and type of ESA treatment. The percentages are to be calculated relative to the number of subjects with available baseline and at least one

post-baseline assessment. The numerator will be total number of subjects with at least one post-baseline PCS ECG value. Shift tables may be presented.

The following Potentially Clinically Significant (PCS) QTc Criteria (both QTcB and QTcF) :

- QTc > 500 msec
- Change from baseline in QTc > 60 msec

will be analyzed in the same way as explained in Section [7.5.2](#) for PCS laboratory abnormalities.

A plot for each parameter of mean (+/- 95% CI) versus visit will be produced by treatment arm (two arms in one page) and type of ESA treatment (darbepoetin alfa and epoetin alfa in another page).

In addition, ECG parameters will be reported according to Astellas standards TEG_003 and TEG_004.

All ECG data will also be listed.

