### **7.5.1 Adverse Events**

AEs will be coded using the Medical Dictionary for Regulatory Activities (MedDRA).

An AE (classified by preferred term) occurring during the treatment period will be considered a TEAE if it was not present prior to the first dose of study drug, or if it was present prior to the first dose of study drug but increased in severity during the treatment period. An AE that occurs more than 28 days after the last dose of study medication will not be counted as a TEAE.

The number and percentage of subjects reporting TEAEs in each treatment group will be tabulated by system organ class (SOC) and preferred term; by SOC, preferred term, and severity; and by SOC, preferred term, and relationship to study medication. If more than 1 event occurs with the same preferred term for the same subject, the subject will be counted only once for that preferred term using the most severe and most related occurrence for the summarization by severity and by relationship to the study medication.

The overall distribution of TEAEs by severity and relationship to study medication will be summarized by treatment group.

The proportion of subjects with TEAEs, fatal SAEs (i.e. events that caused death), and AEs leading to discontinuation of study drug will be summarized by SOC, preferred term and treatment group.

TEAEs will also be reported in terms of cumulative incidence versus time and as an incidence rate per subject-exposure-year.

For the purpose of EU regulatory filing and other submissions: Adjudicated MACE+ events (i.e., myocardial infarction, stroke, death from all causes, hospitalization for chronic heart failure, hospitalization for unstable angina) and other pre specified events will be pooled and analyzed across multiple studies in the global phase 3 program. This analysis will be described in a separate pooled safety statistical analysis plan. For the purpose of US FDA regulatory filing: Adjudicated major cardiovascular adverse events (MACE; i.e., myocardial infarction, stroke, death from all causes) will be pooled across multiple studies in the global phase 3 program to serve as primary safety endpoint. The adjudicated MACE events in this study will be part of this pooled analysis, but will not be a self-contained endpoint within this individual study.

Adjudicated safety data will be reported in a separate report.

Listings will be presented of subjects with SAEs, subjects with AEs leading to discontinuation and subjects who died.

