### 7.5.4 ECGs

Descriptive statistics for ECG parameters (see Section 5.4.5) at BL, and changes from BL, at each assessment time point and for the maximum and minimum value on treatment will be presented by treatment group. The QT interval corrected for heart rate (QTc) will be calculated using both Bazett [ $QTcB = QT/(RR^{1/2})$ ] and Fridericia [ $QTcF = QT/(RR^{1/3})$ ] corrections. Presence of Potentially Clinically Significant ECG values will be reported using similar statistics as mentioned for TEAEs.

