7.5.2 Clinical Laboratory Evaluation

Descriptive statistics for laboratory values (in SI units) and changes from baseline at each assessment time point and for the maximum and minimum on-treatment (i.e., during Safety Emergent Period) value will be presented by treatment arm and treatment for the quantitative laboratory parameters.

Maximum and minimum on-treatment values will be determined using all the original values and not the derived windows.

Shift tables and number and percentage of subjects with shift to low and shift to high will be reported by treatment arm and type of ESA treatment for the quantitative laboratory parameters.

Box plots of quantitative laboratory values (in SI units) versus visit will be produced by treatment arm (two arms in one page) and type of ESA treatment (darbepoetin alfa and epoetin alfa in another page).

Summary by visit for qualitative laboratory parameters will be provided by treatment arm.

All clinical laboratory data will also be listed.

Potentially clinically significant (PCS) laboratory abnormalities

For each potentially clinically significant (PCS) criterion defined in Section 6.2.3.1 the percentage of subjects with abnormalities by visit and at any moment during the Safety Emergent Period and who did not meet the criteria at baseline will be reported by treatment arm and type of ESA treatment.

Incidence rate (per 100 subject years at risk) and the cumulative incidence at .5 year, 1 year, 1.5 years & 2 years with the 95% confidence interval using Greenwood's formula of PCS abnormalities will also be reported, using only subjects who did not meet the criteria at baseline, by treatment arm and type of ESA treatment. Risk of PCS abnormalities will be compared using the same Cox model as used on Section 7.5.1 Hazard ratio and its 95% will be calculated for the frequency of roxadustat as relative to ESA. A dot-and-forest plot will be produced showing the PCS abnormalities above in the y-axis and the incidence rates, the Cox hazard ratio and their 95% CI in the x-axis.

In addition, cumulative incidence plots for subjects experiencing each PCS abnormality will be produced by treatment arm (two arms in one page) and type of ESA treatment (darbepoetin alfa and epoetin alfa in another page).

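### The PCS ECG table in SAP 7.5.4 does not separate new from pre-existing prolongation for QTc >450, QTc >480, QRS ≥150 and PR ≥250 msec

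*SAP*

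**What the plan says.** SAP 7.5.4 tabulates subjects with post-baseline PCS values for the criteria in Tables 9 and 10. On the denominator it says "The percentages are to be calculated relative to the number of subjects with available baseline and at least one" post-baseline assessment. On the numerator it says "The numerator will be total number of subjects with at least one post-baseline PCS ECG value". It then adds "Shift tables may be presented".

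The same section takes two criteria further. QTc >500 msec and QTc change from baseline >60 msec, each under both the Bazett and Fridericia corrections, "will be analyzed in the same way as explained in Section" 7.5.2. Under 7.5.2, the percentage covers subjects with an abnormality "during the Safety Emergent Period and who did not meet the criteria at baseline will be reported", and incidence rates and cumulative incidence are computed "using only subjects who did not meet the criteria at baseline". SAP 7.5.3 applies the 7.5.2 method to all ten combined vital-sign criteria.

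Protocol 7.5.4 says: "Presence of Potentially Clinically Significant ECG values will be reported using similar statistics as mentioned for TEAEs".

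**The concern.** A reader of a table of post-baseline PCS values wants to know whether more subjects developed prolongation on one arm than on the other. As defined, the table mixes two groups: subjects whose interval became prolonged during treatment, and subjects whose interval was prolonged before the first dose and stayed so. The second group says little about treatment, and randomization should make it about equally large in each arm. It therefore adds a similar amount to both percentages and makes them look more alike.

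The SAP applies the remedy elsewhere. It gives no reason for applying the baseline exclusion to laboratory values, vital signs and the highest QTc threshold but not to the lower QTc thresholds, QRS and PR.

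**Working it through.** **Which criteria are affected.** The documents give no ECG rate, so there is no planned figure to reproduce. The first step is to set the rules side by side (criteria from SAP 6.2.5, Tables 9 and 10; methods from SAP 7.5.2 to 7.5.4).

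| Criterion | Can be met at baseline? | Mandatory analysis described in the SAP that excludes subjects meeting it at baseline? |
|---|---|---|
| QTc >450, QTc >480 msec | Yes | No |
| QRS ≥150 msec | Yes | No |
| PR ≥250 msec | Yes | No |
| QTc >500 msec | Yes | Yes, by the 7.5.2 method |
| QTc change >60 msec | No | Not needed; also sent to 7.5.2 |
| QTc change >30 msec | No | Not needed |
| Laboratory PCS | Yes | Yes, 7.5.2 |
| Vital-sign PCS | – | 7.5.2 method applied through 7.5.3 |

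The gap is confined to the first three rows, which hold four criteria. SAP 6.2.5 already categorizes QTc, QRS and PR at baseline, so the exclusion needs no new data.

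**How the mixture acts.** Let b be the proportion meeting the criterion at baseline, r the chance that such a subject meets it again after baseline, and p the new-onset rate among the rest. The percentage in the planned table is

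rate = b·r + (1−b)·p.

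If b and r are the same in both arms, the first term cancels from the difference:

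risk difference = (1−b)·(p_rox − p_ESA).

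The first term stays in both parts of the ratio and pulls it toward 1.

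**Size under assumed inputs.** The values of b, r and p are all assumptions. Take r = 0.9 and new onset of 5% (ESA) against 10% (roxadustat), so the contrast among subjects at risk is 5.0 points and a ratio of 2.00. For b = 10%, ESA is 0.10 × 0.9 + 0.90 × 0.05 = 13.5% and roxadustat is 0.10 × 0.9 + 0.90 × 0.10 = 18.0%.

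| b | Risk difference shown (points) | Risk ratio shown |
|---|---|---|
| 1% | 5.0 | 1.85 |
| 5% | 4.8 | 1.51 |
| 10% | 4.5 | 1.33 |
| 20% | 4.0 | 1.18 |
| 40% | 3.0 | 1.08 |

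With r = 0.7 the ratios are 1.88, 1.58, 1.39, 1.22 and 1.10. With r = 0.9 and new onset of 10% against 20%, the table would show 18% v 27% at b = 10%, 30% v 37.5% at 25%, and 42% v 48% at 40%. Those ratios are 1.50, 1.25 and 1.14 against a true 2.0; the differences are 9, 7.5 and 6 points against a true 10.

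**Subjects without a baseline ECG.** The numerator sentence does not repeat the baseline requirement. Suppose it were read as not nested in the denominator, with 375 per arm and an assumed 20% PCS rate (75 subjects). Then 5, 10 or 20 subjects lacking a baseline would turn 20.0% into 75/370 = 20.3%, 75/365 = 20.5% or 75/355 = 21.1%. That is a small effect even on the literal reading.

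**The case against.** The strongest reply is that the table is descriptive, is labelled post-baseline rather than treatment-emergent, and is surrounded by other ECG output. QTc >500 and change >60 msec have a new-onset analysis with incidence rates, cumulative incidence and Cox hazard ratios. The change criteria are baseline-referenced by definition. Changes from baseline are summarized at each time point and for the maximum on-treatment value, means are plotted with confidence intervals, and all ECG data are listed. Clinically significant ECG abnormalities are also to be reported as adverse events. All of this stands. It rules out the inference that a drug effect on the ECG would be hidden; for four criteria the contrast would be diluted. It does not supply a new-onset count for those criteria.

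Three further readings are tempting, and the documents do not support them.

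- A reader might infer that subjects with no baseline ECG are deliberately counted. The preceding sentence limits the percentages to subjects with a baseline, and SAP 6.2.5 falls back on the screening ECG when Day 1 is missing, so such subjects should be few. This is loose wording, not a counting rule.
- A reader might infer that the protocol requires the treatment-emergent definition, under which an event "will be considered a TEAE if it was not present prior to the first dose of study drug". Protocol 7.5.4 refers to similar statistics, which may mean only counts, percentages and rates. It lends some support but does not decide the matter.
- A reader might infer that nothing else will be reported for these four criteria. SAP 7.5.4 also invokes the sponsor standards TEG_003 and TEG_004. Their content is not in the documents, so they can be assumed neither to close the gap nor to leave it open.

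**Conclusion.** The point holds in a limited form. For QTc >450, QTc >480, QRS ≥150 and PR ≥250 msec, the SAP describes no mandatory analysis that separates new from pre-existing prolongation, and this departs from its own rule in 7.5.2. The direction of the effect is clear if baseline prevalence and persistence are similar across arms: the risk difference shrinks by (1−b) and the risk ratio moves toward 1.

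The size is not known, because the documents give neither b nor any ECG event rate. On the assumed rates it is negligible for the difference and small for the ratio when b is about 1%, and material when b is 20–40%. No confirmatory claim rests on this table and the highest QTc threshold is already handled, so the severity is minor. It is a cheap improvement to safety reporting.

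**What to change.** In SAP 7.5.4:

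1. For QTc >450, QTc >480, QRS ≥150 and PR ≥250 msec, report the number and percentage among subjects who have a baseline ECG not meeting the criterion and one or more ECGs after baseline, in line with 7.5.2.
2. State that the numerator is a subset of the denominator.
3. Change the shift-table sentence from *may* to *will*, and define the shift as baseline category to worst post-baseline category.

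The cost is SAP wording and one table program. Denominators for these rows fall by the baseline prevalence: from 375 per arm to about 371 at b = 1% (375 × 0.99), 300 at 20% (375 × 0.80) or 225 at 40% (375 × 0.60). The mandatory shift table keeps the excluded subjects visible.

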7.5.5 Vascular Access Thrombosis (VAT)

Time to first VAT will be analyzed similarly as in Section [7.5.1.4](#) (Time to event analysis for TEAEs).

7.5.6 Pregnancies

A listing of pregnancy test results will be provided.

7.6 Analysis of PK

The statistical methods for PK data will be described in a separate analysis plan. Results of the population PK analysis will not be reported in the Clinical Study Report but in a separate population PK report.

Plasma concentration data of roxadustat will be listed. In addition, concentration of roxadustat in dialysates will also be listed.

7.7 Analysis of PD

Not Applicable.

7.8 Subgroups of Interest

Selected efficacy and safety endpoints will be summarized for the subgroups defined on the basis of the categorized variables listed below in [Table 26](#)

Table 26 Subgroups of Interest

Grouping variables	Subgroups
Age group	< 65 years 65 - 74 years ≥ 75 years
Sex	Female Male
Previous ESA treatment	Darbepoetin alfa Epoetin
Region	Western Europe Central and Eastern Europe
Baseline Hb	≤11 g/dL >11 g/dL
Dialysis type*	Hemodialysis Peritoneal dialysis
History of cardiovascular, cerebrovascular or thromboembolic diseases #	Yes No
Baseline hs-CRP	≤ULN >ULN

*: Only for primary Hb analyses.

#: This subgroup is derived according to a list of cardiovascular disease preferred terms received from the study physician after softlock.

7.9 Other Analyses

No other analyses are planned.

7.10 Interim Analysis (and Early Discontinuation of the Clinical Study)

The study will have no interim analysis with statistical inference. Safety data and dosing decisions will be monitored on an ongoing basis. Ongoing review of safety data will be completed by an independent Data and Safety Monitoring Board (DSMB).

7.11 Handling of Missing Data, Outliers, Visit Windows, and Other Information

7.11.1 Missing Data

For relevant analyses without rescue therapy, for subjects who used rescue therapy, the reported Hb values after the initiation of rescue therapy will be set to missing (instead of the reported values) for 6 weeks from the start date of rescue therapy (or the end in case the duration of rescue therapy > 1 day).

For response variables, if no Hb value is available during the reference period, an imputation technique will be used, with the mean of all available values from Day 1 to minimum (End of Efficacy Emergent Period, End of the reference period) carried forward.

The following imputations will be performed for the continuous endpoints, unless specified otherwise:

- An MMRM model will be run for the purpose of implicit imputation of missing data by using all the available information from the observed data via the within-patient correlation structure for continuous endpoints with inferential analysis.
- An ANCOVA model with multiple imputations (MI) will also be run (refer to Section 7.4.1.2.1).
- PMM models with different missingness patterns assumptions will be run, in addition (refer to Section 7.4.1.1.2).

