**Table 2 Treatment Arms, Dosing Frequencies and Patient Numbers**

Treatment Arms	Study Treatment	Dosing Frequency	N
1	Roxadustat	TIW	375
2	ESA	Dosing per SmPC	375

TIW = 3 times weekly; ESA = epoetin alfa or darbepoetin alfa; SmPC = Summary of Product Characteristics

During the treatment period, subjects will attend weekly study visits from day 1 to week 8, followed by every other week study visits from week 10 to 36. Following week 36, study visits will occur every 4 weeks until the End of Treatment (EOT).

Randomization and administration of the first dose of study treatment (roxadustat or ESA) is to occur on day 1 which should correspond to a day when their next dose of epoetin or darbepoetin alfa would have been administered.

On day 1 all study procedures and assessments will be completed prior to the first study treatment administration.

During the treatment period, the aim is to maintain the Hb levels between 10.0 g/dL and 12.0 g/dL. All subjects receiving roxadustat will initiate and continue roxadustat dosing at a dosing frequency of TIW throughout the entire period and dose adjustment is to follow prespecified dose adjustment rules [Table 4]. Intake should occur at approximately the same time of day and, if possible, dosing days should remain consistent throughout the study. For HD subjects it is recommended that roxadustat is administered any time after completion of dialysis if dosing is scheduled on a dialysis day to avoid potential bias on certain study assessments. Specific rules apply on the dialysis day(s) at which PK sampling is scheduled [Section 5.6].

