5.3 Per Protocol Set (PPS)

The Per-Protocol Set (PPS) includes all FAS subjects who do not meet any of the reasons to exclude a complete subject from PPS, listed in [Table 4](#). This PPS will be used for the primary EU endpoint analysis, for selected secondary analyses and for all disposition, demography and baseline characteristics.

Table 4 Criteria for excluding a subject from PPS

Number	Reasons for exclusion from PPS
1	Subject who receives less than 12 weeks of study treatment.
2	Subject without a valid corresponding Hb. A valid corresponding Hb is defined as an Hb value from the central laboratory that is measured at least 2 weeks after the first dose and was either before the last study drug intake or at maximum three days after the last drug intake.
3	Prescribed study drug compliance during treatment < 75% during the first 36 weeks analysis period.
4	Violation of inclusion or exclusion criteria which may affect the assessment of the efficacy of the study drug.
5	Administration of wrong randomization study drug for more than one week during the reference period (first 36 weeks) or until EOT, whatever comes first.
6	Administration of prohibited concomitant medication affecting efficacy listed in Appendix 12.1 of the protocol during the reference period (first 36 weeks) or until EOT, whatever comes first.
7	Administration of rescue therapy significantly deviating from the protocol during the reference period (first 36 weeks) or until EOT, whatever comes first.

The selection of subjects for the PPS will be confirmed in the ASC meeting. More details will be provided in the ASC specifications.

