6.1.2 Key Secondary Efficacy Endpoints

The key secondary efficacy endpoints in this study are listed in Table 5

Table 5 Key Secondary Efficacy Endpoints

Number	Endpoint
1	Hb response defined as mean Hb during weeks 28 to 36 within the target range of 10.0 to 12.0 g/dL without having received rescue therapy within 6 weeks prior to and during this 8-week evaluation period.
2	Change from BL in Low Density Lipoprotein (LDL) cholesterol to the average LDL cholesterol of weeks 12 to 28.
3	Mean monthly IV iron use (mg) during day 1 to week 36 (monthly defined as a period of 4 weeks).
4	Change from BL in SF-36 Physical Functioning (PF) sub-score to the average PF sub-score of weeks 12 to 28.
5	Change from BL in SF-36 Vitality (VT) sub-score to the average VT sub-score of weeks 12 to 28.
6	Change from BL in mean arterial pressure (MAP) to the average MAP value of weeks 20 to 28.
7	Time to first occurrence of increase in blood pressure: An increase from BL of ≥ 20 mm Hg systolic blood pressure (SBP) and SBP ≥ 170 mmHg or an increase from baseline of ≥ 15 mmHg diastolic blood pressure (DBP) and DBP ≥ 100 mmHg during weeks 1 to 36.

6.1.2.1 Hb response defined as mean Hb during weeks 28 to 36 within the target range of 10.0 to 12.0 g/dL without having received rescue therapy within 6 weeks prior to and during this 8-week evaluation period.

The average Hb value from weeks 28 to 36 weeks will be calculated as defined below. The Hb response will then be defined as a binary variable, Hb response (Yes/No), where Hb response="Yes" is defined as:

- Average Hb ≥ 10.0 g/dL, and
- Average Hb ≤ 12.0 g/dL.

For this calculation, all available Hb values in weeks 28-36 will be used, i.e. both scheduled and unscheduled Hb values from the central laboratory.

In case a subject does not have any available Hb value in weeks 28-36 (if they died or withdrew from the study for example), imputation rules will be used (refer to Section [7.11.1](#) for imputation rules).

In case a subject requires rescue therapy within 6 weeks prior to weeks 28-36, in weeks 22 to 36, values will be set to missing for 6 weeks after they stopped rescue and will be imputed similarly.

6.1.2.2 Change from BL in Low Density Lipoprotein (LDL) cholesterol to the average LDL cholesterol of weeks 12 to 28.

The analysis will be done on all values (fasted and non-fasted) of Day 1 and up to week 28.

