7.11.6 End of Efficacy Emergent Period

For all subjects, the end of Efficacy Emergent Period is defined as the treatment period up to the EOT Visit. Only exception for subjects who discontinued due to death, the last Hb assessment is taken as per convention the date of death is the EOT visit.

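### The Hb response imputation averages from the pre-dose Day 1 value, so a subject who falls below 10 g/dL and stops before week 28 can be scored a responder in Test 1

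*SAP*

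**What the plan says.** SAP 6.1.2.1 defines Hb response as a mean Hb of 10.0 to 12.0 g/dL over all scheduled and unscheduled central-laboratory values in weeks 28 to 36. "In case a subject does not have any available Hb value in weeks 28-36", with death and withdrawal named as examples, the subject goes to 7.11.1. For rescued subjects, "values will be set to missing for 6 weeks after they stopped rescue and will be imputed similarly".

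SAP 7.11.1 covers response variables whose evaluation window holds no Hb at all. It fills the gap "with the mean of all available values from Day 1 to minimum (End of Efficacy Emergent Period, End of the reference period) carried forward". By SAP 7.11.6, "the end of Efficacy Emergent Period is defined as the treatment period up to the EOT Visit", so for a subject who stops, averaging runs from Day 1 to that visit.

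Four other provisions bear on the result:

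- Protocol 2.2.1.3 places all Day 1 assessments before the first study dose, and SAP Table 32 labels Day 1 as baseline.
- In the same section, "subjects will attend weekly study visits from day 1 to week 8, followed by every other week study visits from week 10 to 36".
- Inclusion criterion 6 requires a mean screening Hb of 9.5 to 12.0 g/dL.
- SAP Table 4 removes from the PPS a "Subject who receives less than 12 weeks of study treatment".

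Test 1 in SAP Table 17 is non-inferiority on the PPS with a margin of -15 percentage points, and it heads a fixed sequence of nine tests. Its sensitivity analyses (SAP 7.4.2.1 and Table 18) change only the analysis set or the rescue handling. The text names All Randomized where the table names FAS.

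**The concern.** The endpoint asks whether Hb is maintained at weeks 28 to 36. For a subject with no usable value there, the rule answers from the whole record since Day 1. The start of that record is largely fixed by the entry criterion, and visits are twice as frequent up to week 8 as afterwards. A subject who loses control of Hb and then stops can therefore be credited with a response on the strength of early values.

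In the roxadustat arm the first weeks may also still reflect pre-study ESA. This is an inference. It is supported by the 2-to-6-week lag between IV epoetin and Hb described in protocol 1.2.3, and by PPS exclusion criterion 2, which accepts an Hb only from 2 weeks after the first dose. It does not carry over to the ESA arm, which continues ESA at about the same weekly dose.

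Crediting failures raises responder rates. If it does so more in one arm, it moves the difference in a non-inferiority test on which eight further tests depend. The EU primary endpoint is stressed by multiple imputation and pattern-mixture models; Test 1 has no comparable check.

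**Working it through.** The documents state no response rate, missing-data rate or power for Test 1, so there is no planned figure to reproduce.

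**Weight of early visits.** Scheduled values fall at weeks 0 to 8 (nine values), then 10, 12, and so on. A stop at week 12 gives 11 values, 9 of them (82%) from weeks 0 to 8. A stop at week 20 gives 15 (60%), and a stop at week 24 gives 17 (53%).

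**Straight-line fall from 11.0 to 9.0 g/dL at the stop** (assumed trajectory). Imputed mean = 11.0 - 2.0 × (mean visit week) / (stop week).

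- Stop at week 12: the visit weeks sum to 36 + 10 + 12 = 58, and 58/11 = 5.27. The mean is 11.0 - 2.0 × 5.27/12 = 10.12.
- Stop at week 20: 126/15 = 8.40. The mean is 11.0 - 2.0 × 8.40/20 = 10.16.

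Both are responders although the last value is 9.0. The mean over the last 8 weeks is 9.76 (visits at weeks 4 to 8, 10 and 12) and 9.40 (weeks 12 to 20), a non-responder each time.

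**Dropping Day 1 only.** Stop at week 12: 58/10 = 5.8, and 11.0 - 2.0 × 5.8/12 = 10.03, still a responder. The early weighting matters as well as the pre-dose value.

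**Rescue** (assumed trajectory). Hb is 11.0 to week 4, then falls in a straight line to 8.8 at week 24 and is 8.8 again at week 26. ESA rescue runs over weeks 26 to 30 and values are blanked to week 36. The 18 remaining values average 10.18, a responder.

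**Where the rule does not misclassify.** A fall from 10.5 to 8.5 gives a mean of about 9.65 with an immediate decline, a non-responder. A fall from 11.0 to 8.5 with an immediate decline gives 9.94 to 9.95 for stops at weeks 16 to 26, also a non-responder.

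**Illustrative effect on the difference.** Assumptions, none from the documents: entry Hb mean 10.8, SD 0.6, truncated to 9.5-12.0; Hb at stop with SD 0.9; visit noise SD 0.4; stops uniform over weeks 12 to 27, all treated as having no value in the window; 200,000 simulated stoppers; the same stopper profile in both arms; more stops on roxadustat. Shift = (share scored responder by the Day 1 mean - share by the last-8-week mean) × (difference in stop rates).

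| Mean Hb at stop | Day 1 mean | Last 8 weeks | Shift, stops 12% v 6% | Shift, stops 20% v 8% |
|---|---|---|---|---|
| 9.0 | 54% | 21% | 2.0 points | 3.9 points |
| 9.5 | 70% | 39% | 1.8 | 3.6 |
| 10.0 | 82% | 60% | 1.4 | 2.7 |
| 10.8 (no average fall) | 94% | 82% | 0.7 | 1.5 |

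With equal stop rates and equal profiles the shift is zero.

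**The case against.** **Scope.** A reader might infer that every PPS subject who stops between weeks 12 and 28 is imputed. The documents do not support that. The rule applies only when no Hb exists in weeks 28 to 36. Subjects who stop still attend visits at EOT + 2 and EOT + 4 weeks, Hb is collected to the end of the study, and the week 28 analysis window opens 7 days early. A subject who stops at about week 24 or later can therefore have a value in the window. Table 32 labels the follow-up visits separately, so the text can be read either way. This stands and narrows the group.

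**Same rule in both arms.** This stands. A reader might infer that Test 1 is biased towards roxadustat, or that its type I error is inflated. Neither is shown, since no rates by arm are given.

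**Stopping is mostly not driven by low Hb.** Of the reasons in protocol 6.1, only a second ESA rescue course is tied directly to Hb. Falling Hb also prompts dose review. This stands and favours the smaller shifts in the table.

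**Cover elsewhere.** Under the SAP, Test 1 is reached only after both EU primary null hypotheses are rejected. The primary endpoint uses the same Hb window under several missing-data models, and discontinuation is tabulated by time and reason. These would reveal many failures, but none tests how the responder classification depends on the imputation.

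**FAS and All Randomized.** Those runs bring in stops before week 12, where early values dominate most, but they are outside the testing sequence.

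**Conclusion.** The point holds in limited form. The SAP's rule can score a subject with failing Hb as a responder in Test 1, and none of the planned Test 1 analyses would show how often it did. That follows from the text and simple arithmetic, and it does not need the ESA carry-over argument: the straight-line examples begin to fall on Day 1.

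The rule can misclassify; it need not. The outcome depends on starting Hb and on the speed of the fall. The size in the trial is unknown. About 1 to 4 points against a 15-point margin rests wholly on assumed stop rates and trajectories, and it vanishes if the arms are alike. No claim is made that the Test 1 conclusion would change. A stated rule of this kind in a non-inferiority endpoint at the head of the sequence should still be corrected and stress-tested.

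**What to change.** 1. In SAP 7.4.2.1 and Table 18, add a sensitivity analysis of Test 1, on PPS and on FAS, that counts subjects with no usable Hb in weeks 28 to 36 as non-responders. It is a deliberately strict bound, because it also fails subjects who stopped with Hb in range.
2. Report by arm how many responses were imputed and how many of those were scored as responders.
3. In SAP 7.11.1, with a cross-reference in 6.1.2.1, exclude the pre-dose Day 1 value. Limit the carried-forward mean to the last 8 weeks of available, non-blanked on-treatment Hb before the stop or, for rescued subjects, before the start of rescue. Eight weeks matches the length of the evaluation period. For a stop at week 12 it still reaches back to week 4, so some early influence remains, which is a further reason for item 1.

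The cost is SAP wording, one extra run on each of the two sets, and possibly slightly lower responder rates in both arms.
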